3.1.1. Phase definitions

The phases in the study will be constructed as follows:

Table 2: Phase Definitions

Phase	Phase #	Period	Period #	Interval	
				From	To
Screening	1			Date and time of signing the informed consent form ^a	One minute prior to start of post-dose period
Vaccination	2	Post-Dose	1	Date and time of vaccination	Minimum of: 
 23:59 on 32 days after the vaccination (23:59 of day of vaccination + 32 days) 23:59 at the date of database cut-off date in case of interim One minute prior to date and time of the challenge 23:59 at the date of last contact (for early discontinuation)
Follow-up Vaccination	3			One minute after Post-Dose period end	Minimum of: 
 23:59 at the date of last contact (for early discontinuation) 23:59 at the date of database cut-off date in case of interim One minute prior to Challenge
Challenge	4	Post-Challenge	2	Date and time of challenge (Study Day 0)	Minimum of: 
 Maximum (28 days after challenge at 23:59, scheduled visit 4 weeks after challenge at 23:59) 23:59 at the date of database cut-off date in case of interim 23:59 at the date of last contact (for early discontinuation)
Follow-up Challenge	5			One minute after Post-Challenge period end	Minimum of: 
 23:59 at the date of database cut-off date in case of interim 23:59 at the date of last contact. (for completed or discontinued subjects)

^a in case an earlier date is available (eg. for lab or vital signs), then use the very first date to include all data

The Follow-up Vaccination phase will only be created in case a subject was challenged to the later than 32 days after vaccination. Moreover, if for one subject no challenge was performed, the Follow-up Vaccination phase should be created and to capture any observations after the Vaccination phase.

3.2. Pooling Algorithm for Analysis Centers

No pooling algorithm will apply, only one site will be used.

3.3. Analysis Sets

Vaccination assignment will follow the as-treated principle.

3.3.1. Full Analysis Set (FA)

The **Full Analysis (FA) Set** includes all subjects who were randomized and received at least one dose of study vaccine, regardless of the occurrence of protocol deviations. All safety analyses will be based on the FA set. As a sensitivity analysis, key immunogenicity tables will also be based on the FA set.

3.3.2. Intent -to-Treat-Challenge Set (ITTc)

The **Intent-to-Treat-Challenge (ITTc)** population is a subset of the FA set that includes all randomized, vaccinated and challenged subjects. All efficacy analyses will be performed on the ITTc population. Important subject information tables might be repeated based on the ITTc population as well.

3.3.3. Immunogenicity Analysis Set

The **Per-protocol Immunogenicity (PPI) Set** will include all randomized and vaccinated subjects for whom immunogenicity data are available, excluding subjects with major protocol deviations expecting to impact the immunogenicity outcomes.

In addition, for subjects who experience a natural RSV infection (based on RT-PCR, or other sources), samples taken after the natural infection will not be included in the PPI set.

The analysis of immunogenicity will be based on the PPI set.

4. DATA MONITORING COMMITTEE REVIEW

An internal data monitoring committee (DRC) will be commissioned for this study, comprised of sponsor personnel not directly involved in the conduct of the study, who have expertise in clinical study conduct and vaccines. There are no planned DRC reviews. The DRC will only convene to discuss any significant or unexpected safety issues. The investigator and SRP will inform the DRC of any AE of concern. In such a case, the study team or DRC members will indicate which analyses are needed, with this SAP serving as a guidance. If deemed necessary for safety review, the DRC may request the randomization codes and review unblinded data, if applicable.

5. SUBJECT INFORMATION

Subject information will be shown for the Full Analysis set.

5.1. Demographics and Baseline Characteristics

Demographic characteristics and screening/baseline characteristics will be tabulated and summarized with descriptive statistics per vaccine regimen and over all subjects.

The following demographic and baseline characteristics will be summarized.

- Sex (Female/Male)
- Age (years)
- Race
- Ethnicity
- Height (cm)
- Weight (kg)
- BMI (kg/m²)

5.2. Disposition Information

The number and percentage of subjects

- screened
- in the FA set
- in the PPI
- in the ITTc set
- randomized, vaccinated and challenged
- randomized, vaccinated and not challenged
- not randomized, not vaccinated
- not randomized, vaccinated
- randomized, not vaccinated

Discontinued subjects (study, vaccination discontinuation and discontinuation from challenge) with the reason of discontinuation will be tabulated per vaccine group and overall.

Also, the number of subjects and percentage per phase will be tabulated.

5.3. Protocol Deviations

Major protocol deviations will be summarized.

5.4. Concomitant Medications

The analysis of concomitant therapies will be done using the WHO drug coded terms.

There will be special attention to analgesics/antipyretics such as acetaminophen, non-steroidal anti-inflammatory drugs (NSAIDs) and aspirin, administered during 8 days following each vaccination (00:00 of day of vaccination + 7 days).

Based on their start and stop date, concomitant therapies will be reported in each applicable phase.

If a concomitant therapy record misses components of its start and/or stop dates (day and/or month and/or year):

- In case of partial start or stop dates, the concomitant therapy records will be allocated to periods using the available partial information, without imputations. If, for example, only month and year are available, these will be compared to the month and the year of the periods, and the concomitant therapy record will be allocated to the period(s) where these date parts match. This rule may lead to assignment to multiple periods.
- In case of a completely missing start date, the concomitant therapy will be considered as having started before the trial.

In case of a completely missing end date, the concomitant therapy will be considered as ongoing at the end of the trial.

6. EFFICACY

6.1. Primary Efficacy Endpoint

The primary endpoint is the area under the viral load-time curve (VL-AUC in \log_{10} copies/ml) of RSV-A Memphis 37b as determined by quantitative RT-PCR assay of nasal wash samples. Nasal wash samples are taken every 12 (± 1) hours beginning two days (ie, in the morning) after inoculation of the challenge virus. VL-AUC is calculated based on the viral load values measured twice daily, starting with the baseline value, and ending with the last available value before discharge.

In the calculation of the AUC, not only the date, but also the timing (the real hours, minutes and seconds as captured in the database should be used, but the AUC result should be reported in hours), of the assessment, is taken into account:

$$AUC\ VL = \sum_{i=2}^T \frac{[VL_{t_i} + VL_{t_{(i-1)}}]}{2} [t_i - t_{(i-1)}] \quad (1)$$

where

t_i = (actual) timepoint i

t_{i-1} = (actual) timepoint $(i - 1)$

T = last timepoint

t_1 = first timepoint after challenge

VL_{t_i} = \log_{10} viral load at (actual) timepoint i

$VL_{t_{(i-1)}}$ = \log_{10} viral load at (actual) timepoint $(i - 1)$

6.1.1. Primary Efficacy Analysis

For this primary efficacy endpoint, the exact Wilcoxon Rank Sum test will be performed and the one-sided p-value will be interpreted at the 5% and 20% significance level, specifically only analysing the statistical significance of a reduction in VL-AUC in the active versus placebo groups.

At the time of database lock of the primary analysis, the results of the quantitative RT-PCR assay will be reported as:

- Either an actual viral load value in \log_{10} copies/mL
- Or ‘Not Quantifiable’ for values below lower limit of quantification (LLOQ).

At the time of database lock of the final analysis, additional detail will be added for the values below the lower limit of quantification and results will be reported at that time as:

- Either an actual viral load value in \log_{10} copies/mL
- ‘Detected’ for value between the lower limit of quantification (LLOQ) and the limit of detection (LOD) of the assay
- ‘Not Detected’ for values below the LOD of the assay

For the primary analysis, values below the LLOQ (indicated as ‘Not Quantifiable’ in the database) will be imputed with 0.

At the time of the final analysis, the same analysis will be repeated, so values below the LLOQ (indicated as ‘Detected’ or ‘Not Detected’) will be imputed with 0.

As a sensitivity analysis at the time of final analysis, the analysis will be repeated but now imputing the ‘Detected’ with $LLOQ/2$ and the ‘Not Detected’ with 0.

These imputations will be used when calculating the AUC based on equation (1). In addition, in case there are missing results in the first timepoint after challenge and/ or the last timepoint after challenge of the AUC, the missing value should be imputed with 0. No other missing values will be imputed.

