5. STUDY VACCINE ALLOCATION AND BLINDING

Study Vaccine Allocation

Within each cohort, subjects will be randomized 1:1 to one of the two groups (Ad26.RSV.preF or placebo). Randomizations will be based on computer-generated schedules prepared before the study by or under the supervision of the sponsor. The randomizations will be balanced by using randomly permuted blocks.

A unique code will dictate the study vaccine assignment for the subject.

Withdrawal of randomized subjects from vaccination before vaccination: Additional subjects will be recruited and immunized to replace these withdrawn subjects at the discretion of the sponsor. The replacement subject will be assigned to the same group as the original (discontinued) subject. The replacement subject's randomization number will equal the randomization number of the discontinued subject +100 (for example subject 0001 would be replaced by subject 0101).

As approximately 44 subjects need to be challenged, initially 4 more subjects in the first cohort will be randomized (overflow subjects). If subjects withdraw between vaccination and challenge, the unblinded pharmacist will make every effort to replace this subject with an overflow subject

of the same group as the withdrawn subject if possible. The withdrawal rate between vaccination and challenge for the first cohort will be used to assess how many extra subjects will need to be vaccinated for subsequent cohorts. Any subject who experiences an SAE before admission to the Unit will not be challenged and will be replaced.

Blinding

The investigator will be provided with a sealed randomization code for each subject, containing coded details of study vaccine allocation. All randomization codes, whether opened or sealed, will be collected after the end of the subject's participation in the study.

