1.2. Trial Design

This is a single center, randomized, placebo-controlled, double-blind Phase 2a human challenge study, to be conducted in approximately 44 healthy male and female subjects aged 18-50 years who have been pre-screened for susceptibility to RSV infection, ie, have levels of RSV neutralizing antibodies compatible with susceptibility to RSV infection.

Subjects will receive single intramuscular doses of 1×10^{11} vp of Ad26.RSV.preF or placebo. More than 44 subjects will be vaccinated to account for withdrawals between vaccination and challenge. The challenge study site, hVIVO, has the capacity to challenge and house under isolation 22 subjects at a time and thus the study will be conducted in several cohorts with up to 22 subjects per cohort. Within each cohort, subjects will be randomized 1:1 to 1×10^{11} vp of Ad26.RSV.preF or placebo. A schematic overview of the study design and groups is depicted in [Table 1](#).

Table 1: Study Design

Group	N	Day -28	Day 0*
Group 1	22	Ad26.RSV.preF (1×10^{11} vp)	Challenge with RSV-A Memphis 37b**
Group 2	22	Placebo	

* ie, not less than 24 or more than 90 days after vaccination.

**Subjects will be challenged in two or more cohorts of up to 22 subjects per cohort. Within each cohort, subjects will be randomized 1:1 to 1×10^{11} vp of Ad26.RSV.preF or placebo.

Note: The infection rate (based on mucus weight, symptoms and viral shedding) in the placebo group will be followed on an ongoing basis by an unblinded individual who does not have any other study function to ensure a sufficient infection rate has occurred. If the infection rate is lower than anticipated, additional subjects may be enrolled, initially four additional subjects in each arm and up to 70 in total. This is to ensure that a high enough number of evaluable subjects is reached in each arm.

For further information related to the design of the study refer to CTP, Section 3.1.

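### Randomisation is within challenge cohort but the primary Wilcoxon test pools the cohorts; if cohort infection rates differ, the test is conservative under 1:1 balance and can lose power, mainly at the 5% level

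*SAP*

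**What the plan says.** Protocol 5 states: "Within each cohort, subjects will be randomized 1:1 to one of the two groups". It adds: "The randomizations will be balanced by using randomly permuted blocks". The block size is not given. SAP 1.2 states: "Subjects will be challenged in two or more cohorts of up to 22 subjects per cohort".

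For the primary endpoint, SAP 6.1.1 states that "the exact Wilcoxon Rank Sum test will be performed", with the one-sided p-value read at 5% and 20%. Protocol 11.4 and the synopsis name the same test. No cohort stratum, covariate or sensitivity analysis appears in either document. The only sensitivity analysis added for the primary endpoint (SAP 2 and 6.1.1) concerns results below the quantification limit.

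Two features of conduct bear on balance. Protocol 3.1 vaccinates 26 subjects for the first cohort, challenges the first 22 vaccinated, and moves overflow subjects to a later cohort. Protocol 5 replaces withdrawals with an overflow subject of the same arm only where that is possible.

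On grouping, SAP 3.3 states above all the analysis sets: "Vaccination assignment will follow the as-treated principle". SAP 3.3.2 then states: "All efficacy analyses will be performed on the ITTc population".

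**The concern.** When allocation is balanced within cohorts, differences between cohorts cannot favour either arm on average. A pooled ranking still counts them as noise, and its reference distribution allows arm-by-cohort imbalances that the design rules out. The result is a p-value that is too large on average and some loss of power. The effect depends on how far cohort infection rates differ, because an uninfected subject contributes an AUC of zero and the zeros are tied.

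The trial has 44 challenged subjects, and its result is also meant to judge the challenge model. The risk is that a real effect misses the 5% threshold, or less often the 20% one. If the realised arms are not balanced within cohorts, the error rate also depends on which way the imbalance happens to fall.

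**Working it through.** **Inputs from the documents** (Protocol 11.2): 22 per arm; placebo mean VL-AUC 320, SD 275; placebo infection rate 65%; one-sided 5% and 20%; at least 80% power for a 50% reduction at 20% and for a 75% reduction at 5%.

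**Assumed, not in the documents:** cohort infection rates (averaging 65%), the distribution of AUC in infected subjects, block size, and how the vaccine acts.

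**Step 1. Reproduce the stated power.** SE = 275 × √(2/22) = 82.9.
- 50% reduction: 160/82.9 = 1.93; 1.93 − 0.84 = 1.09; power 0.86 at 20%.
- 75% reduction: 240/82.9 = 2.89; 2.89 − 1.645 = 1.25; power 0.89 at 5%.

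For simulation, 35% of placebo subjects have AUC 0. Infected mean = 320/0.65 = 492. Infected variance = (275² + 320²)/0.65 − 492.3² ≈ 31,518, so SD 178. The exact test then gives 0.87–0.90 at 20%. At 5% it gives 0.93–0.95 if infection is prevented or both effects act, but 0.755–0.785 if AUC is only scaled down. The stated power therefore reproduces except under pure scaling at 5%.

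**Step 2. Type I error, two cohorts of 11:11.**

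| Cohort rates | Pooled, 5% / 20% | Within-cohort, 5% / 20% |
|---|---|---|
| 65/65 | 5.1 / 19.8 | 5.0 / 19.8 |
| 55/75 | 4.4 / 19.0 | 4.6 / 19.2 |
| 45/85 | 3.9 / 18.3 | 4.9 / 19.9 |
| 35/95 | 2.4 / 16.0 | 4.6 / 20.0 |

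Separate runs for the pooled test give 4.3–4.5 / 19.0–19.5 at 50/80 and 3.3 / 17.2–17.7 at 40/90.

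**Step 3. Power at the two design points (%, pooled → within-cohort).**

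| Cohort rates | 50% reduction, 20%: scaled | same: prevented | 75% reduction, 5%: scaled | same: prevented |
|---|---|---|---|---|
| 65/65 | 85.9 → 85.6 | 88.1 → 87.7 | 75.7 → 75.3 | 94.9 → 94.8 |
| 55/75 | 86.6 → 87.0 | 89.1 → 88.6 | 77.3 → 78.9 | 95.3 → 95.0 |
| 45/85 | 88.6 → 91.4 | 89.4 → 89.3 | 78.1 → 85.2 | 95.6 → 95.5 |
| 35/95 | 91.3 → 96.5 | 90.5 → 90.1 | 81.7 → 94.9 | 97.2 → 97.0 |

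For a 50% scaled reduction at 5%, the separate runs give 65 → 70 at 50/80 and 66 → 79 at 40/90. If the vaccine is all-or-none, the change is −0.5 to +1.5 points.

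**Step 4. Arms unbalanced across cohorts.** Suppose blocks of 4 and challenge in randomisation order. The first 22 are five full blocks plus two subjects, and those two fall in the same arm with probability 2 × (2/4) × (1/3) = 1/3, giving a 10:12 or 12:10 split. Null error at 45/85, with splits written (placebo, active):
- (10,12) then (12,10): pooled about 6% / 24–25%.
- (12,10) then (10,12): pooled about 2–2.5% / 13%.
- The within-cohort test stays at 5.0% / 19.0–19.5% in both.

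Averaged over random imbalance of up to 2 subjects per arm in each cohort, the pooled test gives 4.4% / 18.7%.

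**Step 5. Unequal cohorts.** Take cohorts of 22, 16 and 6 at 45/85/85, a 50% reduction acting both ways, and the 5% level. With van Elteren weights, power goes from 65.6 to 68.4. An unweighted sum of within-cohort rank sums goes from 67.4 to 59.6, so the weights matter. The normal approximation to van Elteren gave null error of 5.3–5.6% / 20.6–21.2% in the three-cohort runs, which is a reason to use the exact permutation distribution.

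**The case against.** The strongest reply is that nothing in the documents says cohorts will differ. There is one site, one strain, one vial and one volume per subject, and one serological entry rule. The interval since vaccination would not be expected to alter placebo infection rates, and the long window serves only a few overflow subjects. This stands: every gap used above is an assumption, and 40/90 is a large one.

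A reader might infer that the primary test is invalid or inflates false positives. The documents do not support that. Under the planned 1:1 cohorts the error never exceeded nominal beyond simulation noise, and it stayed below nominal when averaged over random imbalance. Inflation needs a one-directional imbalance, which permuted blocks and same-arm replacement are meant to limit.

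A reader might also infer that the trial misses its stated power because it ignores cohort. It does not. Power for a 50% reduction at 20% stayed above 80% in every equal-cohort scenario, and the shortfall under pure scaling at 5% is present with identical cohorts too. Protocol 1.2 also points out that complete prevention in some subjects would give an AUC of 0. If the vaccine acts mainly that way, stratifying gains almost nothing.

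Finally, overflow subjects are randomised with one cohort and may be challenged with another, so the stratum has to be defined. That is a fair demand on the remedy. As-treated grouping is a separate matter and causes neither effect.

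**Conclusion.** The point holds as one of efficiency and of matching the analysis to the randomisation. Under exact 1:1 balance the pooled test is conservative: about 4.4% / 19% at 50/80 and 3.3% / 17% at 40/90. The power loss falls mainly at the 5% level and mainly if AUC is scaled down (about 5 and 13 points for a 50% reduction). It is 0 to 4 points at 20%, and about 0 to 1 point under all-or-none protection. With a 12:10 and 10:12 split at 45/85, the pooled error can be about 6% / 25% or 2.5% / 13%, while the stratified test holds 5% / 20%. All of this rests on assumed cohort rates, AUC distribution and mechanism. The change is worth making because it costs little and removes the dependence on how the arms happen to fall across cohorts.

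**What to change.** - **SAP 6.1.1:** replace the pooled test with the exact Wilcoxon test stratified by challenge cohort. Use van Elteren weights 1/(cohort size + 1), permute within challenge cohort, and keep the one-sided 5% and 20% levels.
- **Overflow:** state that an overflow subject challenged later is counted in the cohort in which he or she was challenged. That is the inoculation session shared with the other subjects in the stratum.
- **Sensitivity:** keep the unstratified exact test as a named sensitivity analysis.
- **SAP 6.2.1:** apply the same stratification to the AUC and peak viral load tests.
- **Record and timing:** list the change in SAP 2, because Protocol 11.4 names the unstratified test, and settle it before the treatment codes are requested for the primary analysis.
- **Separate and minor, SAP 3.3:** state that ITTc efficacy analyses use the randomised arm, and keep as-treated grouping for safety. This matters only if a subject receives the wrong injection.

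The cost is a few lines of text and code, and under about 1 power point if the cohorts turn out alike.

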Since preclinical models have suggested some level of protection by the vaccine against nasopharyngeal infection, the study includes a formal primary objective of lowering area under the curve of viral load (VL-AUC), despite the exploratory nature of this study. This VL-AUC has been found in previous studies to be the most sensitive and least variable parameter for efficacy measurement in this model. If the vaccine can prevent infection completely in some subjects, a powerful effect on the AUC would be seen since in those subjects the AUC would be 0. There are also a small number of secondary objectives related to reduction of symptoms

occurring at a specific time, reduction of overall mucous secretion and incidence of infection utilizing more severe or very mild symptoms as alternative definitions, coupled in both cases with two quantifiable RT-PCR measurements to confirm the symptoms are due to RSV.

The statistical approach to this exploratory study is to have an alpha of 20% to indicate a trend and 5% as a significant result for the primary endpoint. If positive results or a trend in the primary or secondary objectives are found, this would suggest that the challenge model may be a reasonable approach to examine vaccine efficacy and would provide evidence to perform more extensive studies. If this study fails its primary endpoint, and does not show any trends in the other endpoints, it would suggest that the human RSV challenge model is not an appropriate model to evaluate potential efficacy of RSV vaccines directed against more serious disease that has more of a lower respiratory component.

Therefore this study will serve as a pilot to explore the value of evaluating RSV vaccines in the human challenge model in RSV vaccine development, with the possibility that, if the model is appropriate, a trend toward efficacy with Ad26.RSV.preF could be detected.

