11.2. Sample Size Determination

[figure not shown]
A sample size of 44 challenged subjects (22 vaccinated and 22 placebo subjects) was chosen as this would provide sufficient evidence to assess if the challenge model is a reasonable approach to examine vaccine efficacy. A multiple of 22 subjects was selected given the capacity of the quarantine Unit.

The sample size was based on the ability to detect trends with a high one-sided alpha (20%), given this is an exploratory study whose partial aim is to determine the utility of the RSV human challenge model for RSV vaccine development. Figure 2 shows the expected power for several reductions in VL-AUC of the quantitative RT-PCR assay, with this selected sample size, a mean VL-AUC in the placebo group of 320 log₁₀ h/mL with corresponding standard deviation 275, an infection rate in placebo of 65% and a one-sided alpha of 5% and 20% based on a Wilcoxon Rank Sum test. This graph suggests that for a one-sided alpha level of 20%, the study has at least 80% power if Ad26.RSV.preF induces a reduction of VL-AUC of the quantitative RT-PCR assay by 50% or more. For a one-sided alpha level of 5%, the study has at least 80% power if Ad26.RSV.preF induces a reduction of VL-AUC of the quantitative RT-PCR assay by 75% or more.

An effect that is significant at 5% (one-sided) will be considered a significant effect. An effect that is significant at 20% (one-sided) will be considered as a trend. This trend, if observed, might be confirmed in future studies.

As this is an exploratory study, the statistical assumptions described above will need to be demonstrated to be correct for the analysis to be conducted as indicated below and as planned in further detail in the SAP. For example, if the infection rate from the study is considerably below 65% then the study will be considered to be underpowered to be able to accurately determine the stated aims. The infection rate in the placebo group will be followed on an ongoing basis by an unblinded individual who does not have any other study function to ensure a sufficient infection rate has occurred. If the infection rate is lower than anticipated, additional subjects may be enrolled, initially four additional subjects in each arm and up to 70 in total. This is to ensure that a high enough number of evaluable subjects is reached in each arm.

Figure 2: Expected Power for Several Reductions in Viral Load

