6.2.1. Secondary and Exploratory Efficacy Endpoint Analysis

For viral loads of RSV-A Memphis 37b as determined by quantitative RT-PCR assay and by quantitative culture of RSV, number of observations, mean, standard error, median, first and third interquartile will be tabulated and means with standard errors will also be graphically presented per time point.

For clinical symptoms scores, total clinical symptom scores, mucus weight and number of tissues, number of observations, mean, standard error, median, first and third interquartile will be tabulated and means with standard errors will also be graphically presented per time point.

For peak viral load based on the quantitative RT-PCR assay, number of observations, mean, standard error, median, first and third interquartile will be tabulated for both groups and graphically presented with boxplots. Exact Wilcoxon Rank Sum tests will also be performed to compare the mean in the active versus placebo groups and the corresponding p-values will be presented. Note the study is only powered for the primary efficacy endpoint and not for any of the secondary one, interpreting these p-values should be done with caution.

For AUCs of viral loads, clinical symptoms and mucus weight, number of observations, mean, median, first and third interquartile (q1, q3) will be calculated for both groups and graphically presented with boxplots. Exact Wilcoxon Rank Sum tests will also be performed to compare AUCs in the active versus placebo groups and the corresponding p-values will be presented. Note the study is only powered for the primary efficacy endpoint and not for any of the secondary one, interpreting these p-values should be done with caution.

Descriptive statistics (number of observations, mean, standard errors, median, q1, q3) of values and changes from baseline for FEV₁, FVC, and FEV₁/FVC will be summarized at each scheduled timepoint. Mean with standard errors of actual values and changes from baseline will also be graphically presented. Finally, spirometry values that are below the clinically important limits, provided in the table below, will be classified as ‘abnormally low’ and the percentage of subjects with ‘abnormally low’ values will be summarized.

Parameter	Clinically Important Limits
FEV ₁	80%
FVC	80%
FEV ₁ /FVC	70%

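### The primary VL-AUC comparison is reported as a p-value with per-arm summaries; no between-group estimate or interval is planned to show how precise a missed trend is

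*SAP*

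**What the plan says.** Protocol 11.4 and SAP 6.1.1 specify one inferential output for VL-AUC: an exact Wilcoxon rank sum test for a reduction, whose "one-sided p-value will be interpreted at the 5% and 20% significance level". The 5% level is labelled significant and the 20% level a trend.

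SAP 6.2.1 states that for AUCs of viral loads, "number of observations, mean, median, first and third interquartile (q1, q3) will be calculated for both groups", with boxplots and p-values. That section covers secondary and exploratory endpoints; I take the sentence to include the RT-PCR AUC as well. It lists no standard error, although the same section lists one for peak viral load. For symptomatic infection, SAP 6.2.1 does plan a difference in proportions with confidence intervals and a forest plot.

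Protocol 11.2 sizes the trial on percentage reductions in VL-AUC: at least 80% power for a 50% reduction at one-sided 20%, and for a 75% reduction at one-sided 5%.

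Protocol 1.2 says that if the primary endpoint fails and the other endpoints show no trend, "it would suggest that the human RSV challenge model is not an appropriate model to evaluate potential efficacy of RSV vaccines". The sentence refers to vaccines aimed at severer illness.

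**The concern.** The trial asks whether the model can show a vaccine effect. A missed trend can mean that the reduction is small or absent, or that 22 per arm was too few to see it. Per-arm means let a reader work out a crude percentage reduction but give no indication of its precision. The quantity on which the trial was sized is therefore never estimated with its uncertainty, while a secondary endpoint does get a difference with an interval.

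At stake is how a non-trend is read. Protocol 1.2 attaches a meaning to it for the whole model, and no planned output on the primary endpoint shows which reductions the data remain compatible with.

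**Working it through.** **Inputs.**
- Sample size (protocol 11.2): "A sample size of 44 challenged subjects (22 vaccinated and 22 placebo subjects").
- Placebo mean (protocol 11.2): "a mean VL-AUC in the placebo group of 320"; the SD stated there is 275.
- Infection rate, alpha levels and test (protocol 11.2): "an infection rate in placebo of 65% and a one-sided alpha of 5% and 20% based on a Wilcoxon Rank Sum test".
- Protocol section 5: "Within each cohort, subjects will be randomized 1:1 to one of the two groups".
- Uninfected subjects are given an AUC of 0. This follows SAP 6.1.1, which imputes values below the LLOQ as 0, and SAP 1.4, which defines the 65% as placebo subjects with detectable virus.

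**Step 1: the plan's own power.** SE of a difference in means = 275 × √(2/22) = 82.9.
- 50% reduction = 160, one-sided 20%: Φ(160/82.9 − 0.842) = 0.862.
- 75% reduction = 240, one-sided 5%: Φ(240/82.9 − 1.645) = 0.894.
- Multiplying the effect/SE ratio by √0.955 for Wilcoxon efficiency gives 0.852 and 0.882.

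Both meet the stated 80%. In simulation with 35% zeros, power for the 50% case was 0.83–0.89. For the 75% case it was 0.76–0.79 if loads are scaled down, 0.82–0.83 if they are shifted, and 0.95–0.96 if infections are prevented. The stated figures are therefore broadly reproduced, with a small shortfall under pure scaling at 5%.

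**Step 2: precision by hand.** The 90% half-width for the mean difference is 1.682 × 82.9 = 139.5, or 44% of 320. On a t-test of means, one-sided p = 0.20 falls at an observed difference of 0.850 × 82.9 = 70.5 (22% of 320). A trial on that boundary has a 90% interval of 70.5 ± 139.5 = −69 to 210, which is −22% to +66% of 320. This illustrates the scale; it is not the Wilcoxon test.

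**Step 3: simulation.** Infected mean = 320/0.65 = 492. Infected SD = √[(275² + 320²)/0.65 − 492.3²] = 178. AUCs in infected subjects are gamma (assumed; the documents give no distribution). The Wilcoxon test is tie-corrected and asymptotic, and the interval is a percentile bootstrap of the percentage reduction in mean VL-AUC, resampled within arm.

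| True reduction | Trials with p > 0.20 | Typical 90% interval | 90% interval includes 50%, given p > 0.20 |
|---|---|---|---|
| 0% | about 80% | −54% to +35% | about 5% |
| 25% | 41–46% | not tabulated | 12% (scaled), 28% (prevented) |
| 50% | 11–12% | 23% to 68% (scaled), 12% to 77% (prevented) | about two thirds (60–67% across runs) |

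The closed formula gives 1 − 0.862 = 14% for the 50% case, close to the simulated 11–12%.

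**Step 4: the two kinds of non-trend.** With no true effect, the interval after a miss almost always excludes a 50% reduction. With a true 50% reduction, it usually includes it. An interval therefore distinguishes many of these cases. A bare p above 0.20 reports both in the same way.

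**The case against.** A reader might infer that the plan condemns the model on the primary p-value alone, or that a negative trial and an inconclusive one cannot be told apart. The documents support neither reading.

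- Protocol 1.2 requires two things, failure on the primary endpoint and no trend elsewhere, and its wording is hedged. Protocol 2.2 asks for careful interpretation. The miss rates above concern the primary endpoint only, so the rate of reaching the negative reading can be no higher and may be lower.
- Protocol 11.2 and SAP 1.4 call the study underpowered if infection is considerably below 65%, and protocol 11.2 allows extra subjects.
- Intervals are planned for symptomatic infection, one of the other endpoints.
- A miss does carry information: p > 0.20 occurs in about 80% of null trials against 11–12% under a true 50% reduction. About 95% of null non-trend trials already have a 90% interval that excludes 50%.

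All of this stands, and it limits the point to what is reported for VL-AUC. It does not close the gap. The infection-rate condition has no numeric cut-off and does not cover imprecision at an adequate infection rate. The protocol synopsis calls secondary endpoints descriptive, and SAP 6.2.1 gives their p-values no trend threshold. None of these safeguards shows the precision of the primary comparison.

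It is also tempting to demand that the model be called unsuitable only when the interval excludes a 50% reduction. The documents do not support that either. Protocol 11.2 uses 50% as a power point and never calls it a minimum worthwhile effect. Taken alone, such a rule could label as unsuitable up to about 10% of trials that do show a trend (true 25% reduction, scaled loads).

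**Conclusion.** The gap is real but limited: the endpoint that carries the formal hypothesis has no planned between-group estimate or interval. At the planned size a miss is common under a true 25% reduction (41–46%) and not rare under a true 50% reduction (11–12%). In the latter case about two thirds of the misses remain compatible with a 50% reduction. This is worth correcting because it bears on the trial's own question. It does not invalidate the test or the design.

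The figures rest on 320/275 describing the whole placebo arm, which is how protocol 11.2 words it, on a gamma shape for infected subjects, and on the 65% infection rate. They also depend on the interval chosen: a 95% interval for the absolute mean difference includes the design effect of 160 in 77–85% of misses under a true 50% reduction. The reason given for Amendment 3 is that the current assay has less granularity at low values than the historical assay behind these assumptions. Realised precision may therefore differ, and an interval would show it.

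**What to change.** Before unblinding, add to SAP 6.1.1 and list in SAP section 2:

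- the percentage reduction in mean VL-AUC, 100 × (1 − mean vaccine / mean placebo), with a two-sided 90% bootstrap interval resampled within arm;
- the Mann-Whitney probability that a vaccinated subject has a lower VL-AUC than a placebo subject (ties counted as one half), with two-sided 90% and 60% intervals;
- a sentence that both are estimates alongside the unchanged Wilcoxon test and its 5% and 20% readings, and that they will be reported whenever a non-trend is interpreted.

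The mean-reduction interval should not be described as matching the rank test. The two target different quantities: in simulation with a true 50% scaling, whether the 90% interval excluded zero disagreed with p ≤ 0.05 in 15% of trials. Resampling within cohort is not advised, because the Wilcoxon test is unstratified and a top-up of four per arm is too small to resample. A Hodges-Lehmann shift is a weak choice here. With about 35% zeros, its simulated estimate was exactly 0 in roughly 33–50% of trials when the true reduction was 0% or 25%.

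The cost is one table and a few sentences, with no change to the test, alpha levels or sample size. The price is that wide intervals will be on view, and a borderline interval may appear to disagree with the p-value and need a line of explanation.
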